6.3.3.2 Mechanistic Assessments

The pharmacodynamic activity of the IMP will be assessed by measurement of biomarkers in blood and serum samples. Relevant parameters will be assessed, including immune markers for effect, relevant T1D parameters and relevant cytokines.

Throughout the study, blood samples will be collected at regular intervals for analysis by the central laboratory, as described in the Visit schedule. Samples intended for mechanistic assessments will be collected from all repeat dose patients in AG019 Cohorts 2 and 4, and from all patients in the combination cohorts

All collected samples will be analyzed by a central lab. Details on sample collection, labeling, storage, shipment and analysis are described in the central lab manual.

Confidentiality Statement

6.3.3.3 Metabolic outcome assessments

Throughout the study, following metabolic outcome assessments will be performed at regular intervals as described in the Visit schedule. Blood samples collected as part of these assessments will be analysed by a central lab:

- Insulin dose adjusted HbA_{1c} (IDAA1c = HbA1c (%) + [4 x insulin dose (U/Kg/24h)]): insulin dose adjusted measurement of glycemic control
- 4h mixed meal tolerance test (MMTT): measure of C-peptide levels, C-peptide area under the curve (AUC) and blood glucose levels after mixed meal stimulation

Details on collection, processing, storage and shipment will be provided in the central lab manual.

6.3.3.1 Mixed Meal Tolerance Test

The MMTT is a liquid meal that is ingested in the fasting state with timed measurements. Also this test is meant to assess the potential participant's insulin production capability. This assessment will be conducted within 21 days of randomization (except for the single dose patients) and at predefined follow-up visits as outlined in the visit schedule. In order for the results to be meaningful, it is important for the participant to follow certain dietary and lifestyle guidelines in the days preceding the test. A high carbohydrate diet must be followed for the three days leading up to the test.

The test should be rescheduled if the participant has a blood glucose (measured on his/her home meter) less than 70 mg/dL (3.85 mmol/L) or greater than 200 mg/dL (11.1 mmol/L).

The participant is required to fast starting the night before the test, and is instructed to consume only water for at least ten hours preceding the test. Long-acting insulin or Basal rates (insulin pump users) will continue as normal. The use of rapid-acting insulin is acceptable up to 2 hours before the MMTT and the use of short-acting insulin up to 6 hours before the MMTT to correct hyperglycemia.

Mixed Meal Dose: The test meal (Boost High Protein) is given at a dose of 6 mL per kilogram body weight. Maximum dose is 360 mL. Boost High Protein is supplied in 8 fluid ounce containers. The Sponsor will supply the test meals.

The MMTT takes approximately four hours to complete, and must be scheduled in the morning (i.e. must be started before 10 AM). It is important to carefully review the eligibility criteria with the participant before starting the test, since if certain criteria have been violated the test will need to be rescheduled for another date.

Procedure: Mixed Meal Dose

Step 1. Ensure the patient is currently fasting

Step 2. Prepping Participant for MMTT

- a. The MMTT must begin between 7:00 10:00 a.m. for proper interpretation.
- b. Obtain the weight of the participant and calculate Boost High Protein meal size = 6 mL/kg, up to 360 mL, 1lb = 0.45 kg

Confidentiality Statement

- c. The MMTT test uses a standard oral mixed meal formula (Boost High Protein) composed of liquid sucrose, soy protein, casein, and soy oil. The test meal is given at a dose of 6 kcal/kg body weight, at 1 kcal/mL to a maximum of 360 kcal.
- d. The participant should remain sitting or resting in bed quietly throughout the test.

 Note: The participant can engage in quiet, non-strenuous activities such as reading, playing cards, watching TV and may walk to the bathroom between blood draws if necessary (but should otherwise remain in resting position until the test is completed).
 - It is recommended that participants not be asked to answer questions for the purpose of completing case report forms during the MMTT.
- e. Place an IV line into an antecubital vein, using an intracatheter/butterfly needle (usually 20 or 22 gauge depending upon the size of the participant). Note: The intracatheter may be kept patent between samples with a slow saline drip or heparinized saline solution (as per the quidelines of your institution) in a 20 mL syringe, injecting about 2-3 mL after each blood draw.
- f. Before the procedure, fill several 3 mL syringes with luer-lock tips with 1 mL normal saline solution to flush the adapter after each blood draw. This is only necessary if the blood sampling is more than 3 minutes apart.

Step 3. Obtain baseline samples:

- a. The first sample should be taken at least 10 minutes after establishing the line(s) and when participant is calm and relaxed (if possible, depending on age) this is the "-10 minute" sample
- b. The second sample should be taken just prior to drinking the Boost High Protein this is the "0 minute" sample
- c. Meal consumption Start the clock at the beginning of the drink. The dose of Boost High Protein must be completely consumed within five (5) minutes.
- d. Obtain post-meal blood samples.
- e. Samples are taken at 15, 30, 60, 90, 120, 150, 180, 210 and 240 minutes
- f. A timer should be turned on at 0 min
- g. The actual start time for each blood draw should be recorded in the patient's source documents and on the Requisition form
- h. Upon completion of the test, the participant should have a snack, for example peanut butter or cheese crackers, coffee, milk or ginger ale.

6.4.Other assessments

6.4.1 Electronic Patient Reported Outcomes (ePRO)

All patients (except for the single dose patients) will be asked to keep an electronic diary. The diaries will contain following information:

Confidentiality Statement

- Safety related information (all experienced adverse events and serious adverse events, including signs of clinical sepsis and known risks associated with the use of anti-CD3 mAb or with T1D glycemic control)
- Occurrence of hypoglycemic events including all relevant information for standard classification (these will be captured separately from other safety related information)
- Deviations from planned study drug intake (e.g. missed doses or incorrect doses taken)
- Changes in concomitant medication intake
- Insulin requirements: Daily

The electronic diaries will be kept from the day of signing the informed consent until the patient is withdrawn or completes the study.

A site research coordinator will train the patients on how to complete the electronic diary.

The research coordinator will review these diaries at every follow-up visit to verify that they have been completed properly and consistently. If needed, the patients will be re-trained on the completion of the diary. All relevant data reported in the diaries will be translated into the eCRF by the research coordinator.

6.4.2Continuous Glucose Monitoring (CGM)

All study patients (except for the single dose patients) will receive a XXX CGM device for the entire duration of their study participation. The investigator will train the patients on how to place the CGM device and will provide written instructions to the patient. The data generated by the device will be downloaded at every site visit. The devices will store data for up to 30 days.

7. STUDY PROCEDURES

7.1. Visit Schedule

The schedule of assessments, evaluations and laboratory studies is presented in XX. A summary of procedures to be performed per visit is given below.

7.2. Single Dose Patients

7.2.1Screening Visit (Day -28 – Day 0)

Following screening observations and procedures will be completed within 28 days prior to randomization:

- Signed and dated ICF
- Assessment against inclusion and exclusion criteria
- Medical history

Confidentiality Statement

- Demographic Data
- Physical Exam
- Vital signs
- 12-lead ECG
- Serum pregnancy test (in females of childbearing potential)
- Blood sampling for local lab (hematology, chemistry, specific screening blood analysis and autoantibodies testing)
- Infectious diseases (EBV, CMV, HIV, HCV, HBV)
- Tuberculosis test
- Drugs of abuse test
- Record concomitant medications
- Record adverse events
- Register patient in IRT
 - Registration in IRT should be done as soon as eligibility is confirmed and ICF is signed.
 Ideally this should be done before the Day 1 visit (start of treatment visit).

7.2.2Treatment Visit (Day 1)

Prior to the first intake of AG019, following observations and procedures will be completed:

- Register visit in IRT
- Physical Exam
- Vital Signs
- Urine pregnancy test (in women of childbearing potential)
- Record Adverse events
- Record concomitant medications
- Administer morning dose of AG019

For Single Dose patients, it is recommended to schedule the Day 1 visit on a Monday, Tuesday or Friday, to avoid having to schedule the Day 4 visit (end of study visit) on a weekend day.

7.2.3End of Study visit (Day 4)

Following observations and procedures will be completed:

- Physical exam
- Vital signs
- 12-lead ECG (only if there is suspicion of cardiac problems)
- Urine pregnancy test (in women of childbearing potential)
- Blood sampling for local lab
- Record Adverse events
- Record concomitant medications
- IMP accountability

Confidentiality Statement

7.3. Repeat Dose Patients

7.3.1Screening Visit (Day -28 – Day 0)

Following screening observations and procedures will be completed within 28 days prior to randomization:

- Signed and dated ICF
- Assessment against inclusion and exclusion criteria
- Medical history
- Demographic Data
- Physical Exam
- Vital signs
- 12-lead ECG
- Serum pregnancy test (in females of childbearing potential)
- Blood sampling for local lab (hematology, full chemistry, specific screening blood analysis, infectious disease, autoantibodies)
- SARS-Cov2 PCR test (only applicable for patients in the combination cohorts)
- Blood sampling for mechanistic assessments (only for repeat dose patients in AG019 Cohorts
 2 and 4 and for patients in the combination cohorts)
- Blood sampling for central lab (HbA1c)
- Blood sample for central lab PK
- Feces collection for central lab PK¹⁰ (only for repeat dose patients in AG019 Cohorts 2 and 4 and for patients in the combination cohorts)
- Tuberculosis test
- Mixed Meal Tolerance Test (MMTT) for C-peptide and glucose assessments
- Drugs of abuse test
- Record concomitant medications
- Record adverse events
- ePRO preparation / explanation
- Assessment of insulin use and hypoglycemic events
- Register patient in IRT
 - Registration in IRT should be done as soon as eligibility is confirmed and ICF is signed to allow for timely shipment of study drug. Ideally this should be done at least 1 week before the Day 1 visit (start of treatment visit).

7.3.2Baseline Visit (Day 1 – start of active treatment)

Prior to the first administration of IMP, following observations and procedures will be completed:

Confidentiality Statement

This document contains confidential information. It is intended solely for the use of the principal investigator, coinvestigators, staff, appropriate institutional review boards or ethical committees, and other required regulatory bodies.

AG019-T1D-101 CSP Final 9.0 11-Jun-2020

¹⁰ Sites should make every reasonable effort to collect feces during the screening visit. If feces cannot be collected during the screening visit, patients will be asked to collect feces between the Screening visit and the Day 1 visit, according to the instructions provided by the site and the collection materials provided by the central lab.

- SARS-Cov2 PCR test (only applicable for patients in the combination cohorts, to be taken within
 3 days before the first teplizumab/placebo infusion)
- Register visit in IRT
- Physical Exam
- Vital Signs
- Urine pregnancy test (in women of childbearing potential)
- Blood sampling for mechanistic assessments (only for repeat dose patients in AG019 Cohorts
 2 and 4 and for patients in the combination cohorts)
- Record concomitant medications
- Record adverse events
- Placement of CGM device, training of patient on how to place the CGM device at home
- ePRO review including insulin use and hypoglycemic events
- Blood sampling for local lab (hematology, full chemistry, INR)
- Evaluation of drug infusion withholding criteria (only for Combination Cohorts)
- Administer first dose of AG019/placebo (for combination cohorts, randomized treatment should be respected)
- First teplizumab/placebo (randomized treatment should be respected)

For patients enrolled in the Repeat Dose AG019 cohorts, it is recommended to schedule the Day 1 visit on a Friday, to avoid having to schedule follow-up visits on weekend days.

For patients enrolled in the Combination cohorts, it is recommended to schedule the Day 1 visit on a Monday, to avoid study drug infusions in 2 consecutive weekends.

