4. STUDY POPULATION

The study population will consist of adults and children who have clinical recent-onset diagnosis of type 1 diabetes mellitus.

Screening for eligible patients will be performed within 28 days prior to the first administration of study drug.

4.1.Sample Size

A maximum of 48 patients will be enrolled in clinical sites in US and Belgium.

In total, 8 single dose patients and up to 48 repeat dose patients⁶ will be enrolled.

Patients who discontinue after entry into the treatment phase may be replaced if approved by the Sponsor. Details about the different cohorts are outlined in Section 5.2.

4.2.Inclusion Criteria

The below tables provide an overview of all inclusion and exclusion criteria which are required to be met for:

AG019 cohorts: column 'AC'

Combination cohorts: column 'CC'

⁶ 4 repeat dose patients will be enrolled per AG019 cohort. In addition, both single dose patients in each AG019 cohort will be offered the option of being re-enrolled as repeat dose patients, provided that no safety concerns have been identified during their participation as a single dose patient. Therefore, if both single dose patients agree to be re-enrolled as repeat dose patients, the maximum number of repeat dose patients per AG019 cohort will be 6.

Confidentiality Statement

This document contains confidential information. It is intended solely for the use of the principal investigator, coinvestigators, staff, appropriate institutional review boards or ethical committees, and other required regulatory bodies.

AG019-T1D-101 CSP Final 9.0 11-Jun-2020

Inclusion Criteria	AC	СС
Male or non-pregnant, non-lactating females, 18-40 (both inclusive) years of age or \geq 12-17 (both inclusive) years of age ⁷ :	Х	Х

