 Females of child bearing potential must have a negative serum pregnancy test at the screening visit, and, if heterosexually active, must use a hormonal (oral, implantable or injectable) method of birth control which remains the same in both nature and dose throughout the study; or have documentation of placement of an intrauterine device or intrauterine system; or use a barrier method of contraception (i.e.; condom or occlusive cap (diaphragm or cervical/vault caps) with spermicidal foam/gel/film/cream/suppository). Females unable to bear children must have documentation of such in the case report form (i.e., tubal ligation, hysterectomy, or post-menopausal [defined as a minimum of one year since the last menstrual period]). Males must agree to not conceive a child during their participation in the study and must agree to use a barrier method of birth control throughout the study (i.e.; condom or occlusive cap [diaphragm or cervical/vault caps] with spermicidal foam/gel/film/cream/suppository), or must have documentation of sterilization (with the appropriate post-vasectomy documentation of the absence of sperm in the ejaculate). 		
 PIG concentration (after 8 or more hours of no caloric intake) ≥126 mg/dL*, or Plasma glucose concentration ≥200 mg/dL 2 hours after ingesting a 75-g oral glucose load in the morning after an overnight fast of at least 8 hours*, or Symptoms of hyperglycemia (e.g., polyuria, polydipsia, polyphagia) and a random (casual, non-fasting) plasma glucose concentration ≥200 mg/dL *In absence of unequivocal hyperglycemia, result to be confirmed by repeat testing 	X	X
Evidence of auto-antibodies to at least 1 of the following β -cell autoantigens: insulin°, IA-2, GAD65, ZnT8	Х	Х
If evidence of autoantibody positivity is documented in the patient's medical file, the assessment does not need to be repeated as part of eligibility verification		
°Insulin autoantibody positivity should be assessed within 10 days following initiation of exogenous insulin treatment.		
Stimulated C-peptide measured during 4h Mixed Meal tolerance Test (MMTT) > 0.2 nmol/L (note: this inclusion criterion does not apply to single dose patients)	Х	х
The first administration of AG019 should occur no later than 150 days post diagnosis.	Х	Х
Body weight ≥ 33kg	Х	Х
Willing and medically able to postpone live vaccine immunizations for at least 8 weeks after randomization		Х

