6.3 Hypotheses and Statistical Methods

6.3.1 Definitions

Baseline Visit 1 is defined as the baseline visit, however if a measurement is retaken at Visit 2 before dosing this will be used as the baseline value instead of the Visit 1 value. This concerns laboratory measurements, vital signs, physical examination and concomitant medication (including insuline use). For fasting glucose baseline is defined as the average of the -10 minute and 0 minute values at screening (Visit 1).

Difference from baseline

The difference from baseline is defined as the difference from the baseline according to the definition above.

Relative day The relative day of an event is derived as:

$$\text{Relative day} = (\text{Start date}) - (\text{Date of first administration of IMP}) + 1$$

For events occurring or starting before the date of first administration of IMP, the relative day is derived as:

$$\text{Relative day} = (\text{Start date}) - (\text{Date of first administration of IMP})$$

In this way, there will be no Day 0. Day 1 is the same day as the day of first administration of IMP, and Day -1 is the day before.

TEAE A TEAE is defined as any adverse event (AE) not present prior to the initiation of the treatment(s) or any AE already present that worsens in either intensity or frequency following exposure to the treatment(s).

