6.3.5 Pharmacodynamic Assessments

Throughout the study, following metabolic outcome assessments were performed:

- Hemoglobin A1c (HbA1c) at Visit 1 and Visit 15-19
- Insulin dose adjusted HbA1c (IDAA1c): insulin dose adjusted measurement of glycemic control calculated as:
HbA1c (%) + [4 x insulin dose (IU/Kg/24h)]. The last collected value of insulin dose will be used for Visit 1-13 and the average for the 3 days before each visit will be used for Visit 14-19

Summary statistics, graphs and listings will be given for the PD variables.

In addition summary statistics for insulin dose per body weight (IU/kg) will be shown per visit. For Visit 14-19 the average use the 3 days before the visit will be used.

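### The only pre-dose HbA1c is taken at screening, up to 28 days before first dose, so change from baseline in HbA1c and IDAA1c includes untreated time

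*Protocol*

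**What the plan says.** Protocol 7.3.1 lists "Blood sampling for central lab (HbA1c" among the screening procedures for repeat dose patients. Section 4 sets the window: "Screening for eligible patients will be performed within 28 days prior to the first administration of study drug". On Day 1 (7.3.2) the pre-dose list has "Blood sampling for local lab (hematology, full chemistry, INR", and mechanistic blood in AG019 Cohorts 2 and 4 and the combination cohorts, but no HbA1c. The local laboratory panel in 6.3.2 does not contain it either. HbA1c is listed again at Days 56, 90, 180, 270 and 360.

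SAP 6.3.5 agrees: "Hemoglobin A1c (HbA1c) at Visit 1 and Visit 15-19". Under SAP 6.3.1 baseline is Visit 1, but "if a measurement is retaken at Visit 2 before dosing this will be used as the baseline value instead of the Visit 1 value". On the scope of that rule the SAP says: "This concerns laboratory measurements, vital signs, physical examination and concomitant medication (including insuline use". IDAA1c is built on "HbA1c (%) + [4 x insulin dose (IU/Kg/24h".

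SAP 7.1 (output section 14.2) tabulates absolute values and change from baseline for both variables; SAP 6.5 plans no adjustment. On time since diagnosis, Protocol 4.2 says: "The first administration of AG019 should occur no later than 150 days post diagnosis". It sets no minimum.

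**The concern.** No HbA1c retake is scheduled at Visit 2, so the replacement rule in SAP 6.3.1 never acts on HbA1c. Haematology, chemistry and (where sampled) mechanistic blood are redrawn before dosing on Day 1; HbA1c, one of the few pharmacodynamic variables this SAP analyses, is not.

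Patients are diagnosed by hyperglycaemia, treated to glucose targets (Protocol 5.1.3) and may enter soon after diagnosis. HbA1c could therefore be moving between screening and first dose. Any such movement would be reported as change from baseline, and it would depend on how soon after diagnosis a patient was screened and how long screening lasted. Phase 1b has no comparator to subtract it.

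There is also a dating question in IDAA1c. Insulin use is reviewed at screening and again before dosing on Day 1, and SAP 6.3.1 names it among the items a Visit 2 value can replace. Baseline IDAA1c could then combine a Day 1 insulin dose with an older HbA1c.

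**Working it through.** The plan gives no figure to reproduce: no assumed HbA1c course, standard deviation or power calculation. Two checks are possible.

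**1. Untreated share of the change interval (documents only).** Day 1 is the first dose and SAP 6.3.1 has no Day 0, so Day *d* is *d* − 1 days after first dose. For a gap of *g* days from HbA1c sample to first dose, the share is *g* / (*g* + *d* − 1). At the maximum, *g* = 28:

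| Visit | Interval (days) | Untreated share |
|---|---|---|
| Day 56 | 28 + 55 = 83 | 33.7% |
| Day 90 | 28 + 89 = 117 | 23.9% |
| Day 180 | 28 + 179 = 207 | 13.5% |
| Day 270 | 28 + 269 = 297 | 9.4% |
| Day 360 | 28 + 359 = 387 | 7.2% |

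The 2-day window around Day 56 moves the first figure between 32.9% (28/85) and 34.6% (28/81). With a 7-day gap the shares are 7/62 = 11.3% at Day 56 and 7/186 = 3.8% at Day 180.

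**2. Size of the drift (assumed rates).** The rate and direction of pre-treatment HbA1c change are not in the documents. Assume a linear fall of *r* points per 30 days and no drug effect. The pre-dose part is *r* × 28/30, and the Day 56 change is *r* × 83/30 from screening or *r* × 55/30 from Day 1:

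| Assumed fall per 30 days | Pre-dose part, 28-day gap | Day 56 fall from screening | Day 56 fall from Day 1 |
|---|---|---|---|
| 0.1 | 0.09 | 0.28 | 0.18 |
| 0.25 | 0.23 | 0.69 | 0.46 |
| 0.5 | 0.47 | 1.38 | 0.92 |
| 1.0 | 0.93 | 2.77 | 1.83 |

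If HbA1c is flat, the pre-dose part is 0. If it rises by 0.2 per 30 days, the part is −0.2 × 28/30 = −0.19, and a real fall on treatment would be understated. With a 7-day gap the range for falls of 0.1 to 1.0 is 0.02 to 0.23. HbA1c enters IDAA1c with weight 1, so the same amounts carry over.

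**Dating of IDAA1c.** SAP 6.3.1 lets a Visit 2 insulin value replace Visit 1. SAP 6.3.5 uses the last collected insulin value for Visits 1–13 without saying which visit supplies the dose for baseline IDAA1c. The weight on insulin is 4, so a difference of 0.1 IU/kg/day between the two visits moves baseline IDAA1c by 4 × 0.1 = 0.4.

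**Comparators.** Ten patients per combination cohort are randomised 4:1, giving 10/5 = 2 on placebo per cohort and 4 in all. Phase 1b has none.

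**The case against.** Several objections stand and limit the point.

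- **Falling HbA1c is an outside assumption.** A reader might infer that pre-treatment decline is certainly being counted as response. The documents give no HbA1c course, and a patient near the 150-day limit could be flat or rising.
- **28 days is a maximum.** Protocol 6.3.3 puts the baseline meal tolerance test, also a screening procedure, within 21 days of randomisation. If HbA1c is drawn on the same day, the gap is about 21 days or less, and the Day 56 share is at most about 21/76 = 27.6%. Nothing requires the same day, so 28 days remains possible.
- **A Day 1 sample is a partial cure.** The table shows that under a steady fall more of the Day 56 change arises after Day 1 than before it. Without a control, that part would still appear as change from baseline.
- **It is late for many patients.** The SAP describes enrolment in the past tense, and SAP 6.9 reports a second interim analysis as done. Under Protocol 10.8 that analysis follows Day 180 for all of Combination Cohort 1 and the two open-label patients of Combination Cohort 2.
- **Dates are already to be listed.** SAP 6.3.3 puts the date and relative day in listings, and individual HbA1c plots are planned. The gap can be recovered patient by patient, although no table uses it.
- **The mixed-date IDAA1c is one reading.** Visit 1 HbA1c with Visit 1 insulin is equally natural. The text permits both and settles neither.

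A reader might also infer a biased comparison with placebo. Randomised patients in both arms share the same screening window, so that contrast is unbiased in expectation; with 2 placebo patients per cohort it is only very imprecise.

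**Conclusion.** The structural point holds on the documents alone: the screening HbA1c is the scheduled baseline for both variables, and up to 34% of the Day 56 interval and 13.5% of the Day 180 interval is untreated time. The amount of HbA1c drift this carries is unknown: 0.09 to 0.93 points over 28 days for assumed falls of 0.1 to 1.0 per 30 days, zero if HbA1c is flat, and the opposite sign if it rises.

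The effect is confined to descriptive, unadjusted secondary summaries. It matters most for within-group change in Phase 1b. The primary endpoint (treatment-emergent adverse events to six months) is untouched. The rule for baseline IDAA1c is ambiguous, which is less than a demonstrated error. This is an optional improvement.

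**What to change.** **Patients not yet dosed.** Add "Blood sampling for central lab (HbA1c" to the pre-dose list in Protocol 7.3.2, and change the HbA1c line in SAP 6.3.5 to Visit 1, Visit 2 and Visits 15–19. The existing rule in SAP 6.3.1 then makes the Day 1 value the baseline with no further wording, and the untreated part of the interval falls from up to 28 days to 0.

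**Patients already dosed.** State in SAP 6.3.5 that baseline IDAA1c uses HbA1c and insulin dose from the same visit. Beside the HbA1c and IDAA1c change tables, summarise days from HbA1c sample to first dose by cohort and treatment group.

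**Cost.** One extra central-laboratory tube per patient at a visit where blood is already drawn, a short SAP edit and one summary row. The change removes pre-dose drift only; natural change after Day 1 stays in the uncontrolled summaries and should be stated as a limitation.
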